9.5.2 Phase II Analysis

9.5.2.1 Primary analysis

At the final analysis (which occurs after 12 months of follow-up after the last patient is enrolled), a one-sided p-value is calculated for a stratified logrank test comparing treatment versus control. This corresponds to a formal test of the null hypothesis that the survival (event free) distribution of the treatment group is less than or equal to the survival distribution of the control group, i.e.

$$\begin{aligned} H_0: S_T(t) &\leq S_C(t) \\ H_a: S_T(t) &> S_C(t) \end{aligned}$$

where $S_T(t)$ and $S_C(t)$ are the survival distributions for the treatment and control groups, respectively, and $t > 0$ denotes observation time. The stratification factors for the test include

previous PFI (6-12, 12-24 months), BRCA status (known positive versus other) and prior lines of platinum-based treatment (1,2). The treatment will be considered superior to control if the corresponding one-sided p-value is less than or equal to 0.023. If the p-value is greater than 0.023 but less than 0.10, there may be sufficient promise to conduct another trial. The significance level of 0.023 is selected to control the overall Type I error of the adaptive design to be less than 0.025, as shown via simulation.

9.5.2.2 Secondary analysis

Tumor response data will be summarized at each tumor assessment cycle using the following response categories: Complete Response (CR), Partial Response (PR), Stable Disease (SD), Progressive Disease (PD) and Non-Evaluable (NE). Best overall response for a patient is the best response recorded from the start of the treatment until disease progression or death. Best overall response will be summarized as the number (%) of patients in each category of response (CR, PR, SD, PD, and NE). PR and CR must be confirmed by a repeat assessment at least 28 days after the criteria are first met for the response to be considered a PR or CR.

The overall response rate is defined as the percentage of patients with a confirmed response of CR or PR in a given population.

The duration of response (confirmed CR or PR) is defined as the number of days from the date of initial response (not the confirmation date) to the date of objective disease progression or death due to any cause, whichever occurs first. If neither event occurs, duration of response will be censored at the date of the last evaluable tumor assessment. Symptomatic deterioration is not objective disease progression.

Overall survival (OS) is defined as the number of days from the date of randomization to the date of death. In the event of no death, overall survival will be censored at the last known alive date.

PFS by assessment of CA-125 will be analyzed. CA-125 progression is defined according to the Gynecologic Cancer InterGroup (GCIG) criteria. The relationship between CA-125 progression and radiological disease progression will be evaluated.

PFS, OS and duration of response will be analyzed using Kaplan-Meier methodology. Kaplan Meier curves will be plotted. Median survival and duration times will be estimated and their 95% confidence intervals based on Brookmeyer-Crowley methodology will be calculated. In addition, hazard ratios and 95% confidence intervals will be provided. For the overall response rate and categorical response rates, 95% confidence intervals will be calculated based on Clopper-Pearson methodology.

9.5.3 Pharmacokinetic Analysis

APR-246 concentrations will be determined by a validated HPLC tandem mass spectrometry

(LC/MS/MS) method and calculated PK parameters (Cl, Vss, C_{max}, AUC₀₋₂₄, AUC_{0-∞} and t_{1/2}) of APR-246 will be determined.

Individual and mean profiles of APR-246 concentrations will be presented graphically. Protocol-specified blood sampling times will be used in the graphical presentation.

No formal statistical analysis beyond descriptive statistics is planned. For each PK parameter, individual and mean data and summary statistics (including number of patients, arithmetic mean, geometric mean, SD, CV, median, Min and Max) will be presented.

9.6 Randomization/Stratification

In Phase II, patients will be centrally randomized in a 1:1 ratio to receive the carboplatin/PLD chemotherapy regimen with or without APR-246. Permuted block randomization will be used to randomize patients to study treatment. Study treatment will not be blinded.

The stratification factors to be used are:

- Platinum-free interval after previous platinum based regimen. >6-12 months vs. >12 to <24 months
- Prior Lines of Platinum Treatment. One line vs. two lines
- BRCA status. Known positive vs. Other

9.7 Statistical Modeling for Interim Analyses

Although the final analysis for the primary endpoint is a frequentist (stratified logrank) test, the model underlying the adaptive sample size selection is Bayesian in nature. As shown via simulation in the Appendix V, the design has control of Type I error rate.

9.7.1 Control Hazard Model

Let T_i be the progression event time (in months) for the primary endpoint for the i th patient, where an event represents a negative outcome for the patient. We model the event times for the control arm as piecewise exponential:

$$T \sim PE(\Lambda),$$

where $\Lambda = (\lambda_1, \lambda_2, \lambda_3, \lambda_4)$ represents the set of baseline hazard rates (events per month) within each segment. The hazard is assumed to be constant within each segment, s , and modeled with prior

$$\lambda_s \sim \text{Gamma}(a_s, b_s),$$

where the gamma distribution has the following density function:

$$p(\lambda_s) = b_s^{a_s} \lambda_s^{a_s-1} \exp(-b_s \lambda_s) / \Gamma(a_s).$$

The 4 segments of the model are defined in Table 17, along with the parameters of the non-informative prior distributions.

Table 17. Prior Parameters for the Control Hazard Model

Segment (s)	Interval(months)	a_s	b_s
1	0 - 6	1	1
2	6 - 12	1	1
3	12 - 18	1	1
4	18 - ∞	1	1

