2.2 Disease Background

Ovarian cancer is the seventh most commonly diagnosed cancer among women in the world, accounts for an estimated 239,000 new cases and 152,000 deaths worldwide annually [6]. Ovarian cancer has been of considerable interest to clinical cancer investigators due to the fact that it is among the most chemosensitive of all solid tumors [7]. It is frequently platinum sensitive initially and even in advanced disease the accepted management is a combination of surgery and platinum based chemotherapy.

Despite the evolution of surgical techniques and ever improving chemotherapy regimens, relapse and consequential disease progression remains the most challenging task. Screening has not yet proven an effective tool to diagnose patients at an earlier stage in their disease and late diagnosis is associated with relapse and death after repeated treatment cycles. The 5 year survival rate remains poor at less than 40% and this has remained unchanged for the last 20 years [6]. Thus, there is a need for improved treatment of relapsed ovarian cancer. The combination of carboplatin and pegylated liposomal doxorubicin is widely used in Europe following results of the multicenter phase III CALYPSO study which demonstrated non-inferiority of this combination over the standard carboplatin and paclitaxel combination arm in terms of PFS (11.3 months versus 9.4) with lower rates of severe and long-lasting side effects [8].

Despite rapid scientific advances in the last decades, it has proved difficult to improve outcomes beyond platinum-based therapy introduced in the late 1970s. Cisplatin, and subsequently carboplatin has been combined with other agents, especially taxanes to form the backbone of current treatment regimes. The combination is effective in first-line, platinum sensitive ovarian cancer, but unfortunately since most patients are diagnosed late, recurrence is common. Drug resistance does eventually develop due to repeated treatment with the same drugs. With each relapse, the response to treatment decreases with lower quality of life.

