2.7 Rationale for the Current Study

HGSOC accounts for approximately 70% of malignant surface epithelial carcinoma in Europe and North America [9]. Clinical data shows that TP53 mutations are present in at least 96% of patients with HGSOC [4]. Furthermore, TP53 mutations have been shown to correlate significantly with resistance to chemotherapy, early relapse and shortened overall survival [11].

Despite the evolution of surgical techniques and ever improving chemotherapy regimens, relapse and consequential disease progression remains the most challenging task for ovarian cancer patients. The combination of carboplatin and pegylated liposomal doxorubicin has shown an improvement in PFS (11.3 months versus 9.4) with lower rates of severe and long-lasting side effects, and has been accepted as standard of care for patients with platinum-sensitive ovarian cancer, including HGSOC [8].

APR-246 may offer an opportunity to improve current treatment of HGSOC. The rationale for this derives from preclinical evidence that APR-246/MQ (i.e., the active moiety of APR-246) induces apoptosis and cell death in cancer cells with mutant or otherwise non-functional p53. Additional to the apoptosis-inducing effect as a single substance, APR-246 can act synergistically with platinum compounds by reversing the cisplatin sensitivity of cisplatin-resistant TP53 mutant ovarian cancer cell lines, resulting in resensitization of cancer cells to cisplatin.

The completed Phase I/II extended exposure study of single agent APR-246 (APR-246-01 Amendment 6) indicated that prolonged exposure, after 4-hour and 6-hour pulse incubations as compared to 2 hours, resulted in stronger apoptotic response. Ten patients have received 6-hour infusions and pharmacokinetic, safety and efficacy parameters have been collected. No major safety concerns were reported, and 2 patients have shown protocol defined clinical responses.

This study also provided important information about APR-246 and increased knowledge about its safety and tolerability, as well as pharmacokinetic (PK) and optimal administration. In summary, the results of the extension study suggested that the adapted dose regimen was suitable and that APR-246 was well tolerated with limited number of adverse events. The pharmacokinetic data suggested time-independent and dose-independent kinetics.

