9.7.2 Model

The event times for the treatment group is also modeled as piecewise exponential, with hazard rates $h_s = \lambda_s \exp(\theta)$,

where θ is the log hazard ratio for treatment relative to control. By convention, hazard ratios less than one indicate treatment benefit. The log hazard ratio has the non-informative prior

$$\theta \sim N(0, 0.5^2),$$

and is assumed to be constant over time.

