9.7.3.2 Predictive Probability of Success

At each interim analysis, we also calculate the predictive probability of success (PPoS) if accrual is halted at the current sample size and all patients are followed for a minimum of 12 months. For each iteration in the MCMC algorithm after burn-in, event times are imputed for each patient without an observed event among patients current enrolled, creating a single imputed data set for each MCMC iteration. A stratified logrank test is performed on each imputed data set, and PPoS is equal to the proportion of imputed trials with a one-sided p-value less than 0.023.

Although not currently included in the simulations, PPoS will also use longitudinal modeling of CA-125 to better inform the predictive probability calculation. Neither the CA-125 data nor the longitudinal model will be included in the final analysis; rather the data are used to better inform the

decision of stopping accrual for predicted success.

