9.8.3.2 Stopping for Small Observed Effect

At each interim analysis beginning at 150 patients enrolled, the trial may stop enrollment early for a small observed effect size if

$$\text{Pr}(HR < 0.8) < F_n$$

where $F_n = 0.30$ for each interim. If this stopping rule is met, the Sponsor will be informed by the DSMB that the study has reached a stopping boundary for a small observed effect. The Sponsor may then choose to unblind data and release results prior to 12 months after the last patient is enrolled. If

data are unblinded and results are released, regulatory approval will not be sought and results may be used for the planning of future trials. Otherwise, the Sponsor may choose to continue to follow currently enrolled patients in a blinded manner until 12 months after the last patient is enrolled.

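### Do the interim priors, labelled non-informative but in fact informative, distort the accrual-stopping rules enough to need replacing?

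*Combined protocol and SAP*

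**What the plan says.** Section 9.7.1 models control PFS as piecewise exponential over 0-6, 6-12, 12-18 and 18+ months. The parameter vector "represents the set of baseline hazard rates (events per month) within each segment". Table 17 sets a = b = 1 in all four segments, and the gamma density is written in rate form. The text adds: "The 4 segments of the model are defined in Table 17, along with the parameters of the non-informative prior distributions". Section 9.7.2 multiplies these hazards by a constant hazard ratio. "The log hazard ratio has the non-informative prior", namely normal with mean 0 and SD 0.5.

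Two accrual rules use this model.

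- Small effect (Section 9.8.3.2): from 150 patients, "the trial may stop enrollment early for a small observed effect size if" the posterior Pr(HR < 0.8) is below 0.30.
- Predicted success (Sections 9.7.3.2 and 9.8.3.1): from 200 patients, accrual may stop if PPoS exceeds 0.95. For PPoS, "event times are imputed for each patient without an observed event among patients current enrolled", and each completed data set is tested by stratified logrank at one-sided 0.023. "Although not currently included in the simulations, PPoS will also use longitudinal modeling of CA-125".

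The final analysis (Section 9.5.2.1) is a one-sided stratified logrank test at 0.023, 12 months after the last patient enrols. That level was chosen by simulation. Section 9.8.4 gives power of about 0.70 at HR 0.70.

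Sections 2.2 and 2.7 report median PFS of 11.3 months for carboplatin/PLD and 9.4 for its comparator in a cited phase III study. No readable section gives a control median for this trial, and the simulation appendix (Appendix V) is blacked out.

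**The concern.** On the monthly scale, Gamma(1,1) says that the typical control patient progresses in about a month. It gives only about 6% probability to a hazard as low as the one implied by the cited carboplatin/PLD result. The normal prior gives Pr(HR < 0.8) = 0.33 before any data, close to the 0.30 stopping limit. Calling either non-informative suggests that nobody checked the scale.

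The worry has substance because both accrual rules run on this model and the looks are timed by enrolment. With brisk accrual there is little follow-up beyond 12 months at the 150 and 200 looks. The imputation in the late segments then comes largely from the prior and creates events that will not occur. PPoS could look too high, accrual could stop too soon, and small-effect stops could be too rare. Final power would suffer through the sample size reached.

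**Working it through.** **Inputs.** From the documents: the priors, stopping limits, looks, 1:1 allocation, maximum 400, one-sided 0.023, 12 months' minimum follow-up. Assumed: exponential control PFS with median 11.3 months (the cited study's figure) and accrual of 6, 10 or 15 per month unless stated. Not modelled: strata, scan schedule, dropout, CA-125 model.

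**1. The plan's power figure.** Schoenfeld events for HR 0.70 and power 0.70: 4(1.995 + 0.524)²/(ln 0.70)² = 25.4/0.127 ≈ 200. Simulating the stopping rules with the Table 17 priors gives power 0.78/0.73/0.67 at 6/10/15 per month (2,000 trials per cell). The stated 0.70 lies in this range, but it cannot be reproduced exactly without the accrual and control hazard behind it.

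**2. Centre and weight of the priors.**

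- Gamma(1,1): mean 1/1 = 1 per month. ln2/11.3 = 0.0613, ratio 16.3. For 9.4 months, 0.0737 and 13.6. For assumed medians of 6 to 18 months the ratio runs from about 9 to 26.
- N(0, 0.5²): precision 1/0.25 = 4. Each event carries about 1/4 under 1:1 allocation, so 4/0.25 = 16 events. Prior Pr(HR < 0.8) = Φ(ln 0.8/0.5) = 0.33.

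**3. How fast data outweigh the hazard prior.** Gamma(1,1) equals one event in one patient-month. With E patient-months at a true 0.0613, the posterior mean is (1 + 0.0613E)/(1 + E). Relative to the truth this is 1.7 times at E = 20, 1.15 at 100 and 1.03 at 500. The factor of 16 applies only where there is no exposure.

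**4. Effect on the interim HR.** With equal exposure per arm, a segment shifts the log-HR score by about −0.5(1 − 0.0613)·E/(1 + E) = −0.469·E/(1 + E). Dividing the sum by the information D/4 + 4 gives the shift in log HR. Simulated mean exposure and events at 10 per month, HR 1:

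| Look | E by segment | D | Shift in log HR | HR multiplied by |
|---|---|---|---|---|
| 150 | 608, 212, 20, 0 | 52 | −1.38/17.0 = −0.081 | 0.92 |
| 200 | 858, 385, 122, 6 | 85 | −1.80/25.25 = −0.071 | 0.93 |
| 350 | 1609, 905, 482, 341 | 206 | −1.87/55.5 = −0.034 | 0.97 |

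Simulation against Gamma(1,16) agrees: 6-8% lower at 150, 5-7% at 200, 3-4% at 350.

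**5. Effect of the log-HR prior.** It shrinks towards 1. An observed 0.70 on 50 events becomes exp(−0.357 × 50/66) = 0.76; on 150 events, exp(−0.357 × 150/166) = 0.72. When treatment works, this opposes step 4.

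**6. Projected against actual final events, 200 look.**

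- HR 1: 160 vs 159, 156 vs 145, 168 vs 135 (+1%, +8%, +24%).
- HR 0.70: 149 vs 148, 147 vs 132, 161 vs 122 (+1%, +11%, +32%).

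At 15 per month the HR 1 excess falls to 16% at the 250 look and 7% at 300. It is larger with faster accrual: a separate run at 25 per month gave 175 vs 124.

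**7. What reaches the decisions** (6/10/15 per month; PPoS gap = mean PPoS minus realised success at the 200 look):

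| | Table 17 priors | Gamma(1,16) only | Gamma(1,16), N(0,1), limit 0.25 |
|---|---|---|---|
| Power, HR 0.70 | 0.78/0.73/0.67 | 0.70/0.65/0.59 | 0.77/0.72/0.67 |
| Power, HR 0.60 | 0.95/0.92/0.88 | – | 0.94/0.92/0.89 |
| Mean N, HR 0.70 | 277/292/300 | – | 275/291/303 |
| Small-effect stops, HR 1 (%) | 92/90/87 | 95/95/93 | 93/91/88 |
| Type I error (SE 0.003) | 0.021/0.019/0.018 | – | 0.020/0.017/0.018 |
| PPoS gap, HR 0.80 | +0.07/+0.13/+0.17 | +0.04/+0.05/+0.06 | +0.05/+0.08/+0.10 |
| PPoS gap, HR 0.70 | +0.01/+0.03/+0.07 | −0.02/−0.05/−0.04 | −0.01/−0.02/0.00 |
| PPoS gap, HR 0.60 | −0.07/−0.08/−0.07 | −0.09/−0.14/−0.17 | −0.08/−0.11/−0.12 |

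Final success after a success stop, Table 17 against the third column: HR 0.70, 0.984 vs 0.989 at 6 per month and 0.953 vs 0.956 at 15; HR 0.80, 0.952 vs 0.960 and 0.875 vs 0.882; HR 0.60 at 15 per month, 0.992 vs 0.993.

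A further simulation gave power at HR 0.70 of 0.777 vs 0.768 at 10 per month and 0.743 vs 0.737 at 15. Its levels are higher than those in the table, so only differences within a run are used here.

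**The case for a change.** The strongest case for a change is that the mislabelling is certain, the over-projection is real, and correcting both costs some wording and one simulation run. Section 9.7.3.2 already says that the CA-125 model is outside the simulations, so another run would be natural. With Gamma(1,16), projected events at HR 1 become 158/142/131 against 159/145/135 actual. At the 200 look alone, the small-effect boundary at HR 1 is met in 66/58/61% of trials under Table 17 and 78/73/72% under Gamma(1,16).

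The label and the over-projection stand as facts. The case for new priors does not.

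- The single-look gap largely closes over the trial: small-effect stops at HR 1 end at 92/90/87% against 95/95/93%. Those 3-6 points cost about 8 points of power at HR 0.70.
- Changing the normal prior and the small-effect limit as well recovers that power, but arrives at the operating characteristics that Table 17 already has. PPoS is closer to realised success at HR 0.70 and 0.80 and further from it at HR 0.60. Mean PPoS need not equal realised success at one fixed HR in any case.
- The 16-fold ratio borrows another trial's median. That study's title specifies late relapse, whereas this trial enrols progression 6-24 months after a first or second platinum regimen. If the control median were 7 months (assumed; 10 per month, HR 0.70), simulated power is 0.789 with Table 17, 0.749 with the recalibrated set and 0.692 with Gamma(1,16) alone. A prior tuned to 11.3 months could do harm.

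**Conclusion.** No change follows. The label is a loose word for two weakly to moderately informative priors; removing it alters nothing that the trial computes or decides. The hazard prior weighs one event per segment. It lowers the interim HR by about 3-8% and inflates projected events only where late follow-up is thin. The log-HR prior pulls the other way under benefit.

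Against a recalibrated set, power at HR 0.70 differs by at most 0.01, mean N by at most 3, small-effect stops at HR 1 by 1 point, and success after a success stop by at most 0.008 in the cells listed in step 7. Simulated Type I error was 0.017-0.025 under all prior sets and accrual rates tried, with Monte Carlo error. Correcting the hazard prior alone would make the design worse. The final test is free of both priors, so the remaining influence is only on when accrual stops.

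This rests on assumed exponential control PFS with median 11.3 months and mainly on accrual of 6-15 per month. At 20 per month and HR 0.70, a separate run of 600 trials gave final success 0.63 with the plan's priors and 0.61 with a centred hazard prior and a diffuse log-HR prior, so the conclusion held there too. The stated power of about 0.70 may already include these priors through Appendix V, which cannot be read; nothing is held against the plan for that.

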9.7.2 Model

The event times for the treatment group is also modeled as piecewise exponential, with hazard rates $h_s = \lambda_s \exp(\theta)$,

where θ is the log hazard ratio for treatment relative to control. By convention, hazard ratios less than one indicate treatment benefit. The log hazard ratio has the non-informative prior

$$\theta \sim N(0, 0.5^2),$$

and is assumed to be constant over time.

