The median survival time for patients with advanced HGSOC is approximately 44 months. In platinum-sensitive cancer, tumor response to first line platinum-based treatment lasts at least 6 months following initial treatment. In the first line setting, carboplatin, generally in combination with a taxane provides impressive results with about a 70% response rate. Patients are retreated at relapse with platinum unless the cancer is platinum resistant (i.e. tumor progression within 6 months after completing first line treatment). Unfortunately almost 50% of Epithelial Ovarian Cancer (EOC) patients will relapse within 18 months and 75% by 30 months. The likelihood that a patient will respond to the reintroduction of a platinum-based regimen depends on the platinum-free interval (PFI), defined as the interval between the last dose of platinum and the time of relapse. Thus, fewer patients with a PFI of 6–12 months are expected to respond to the reintroduction of platinum-based chemotherapy, compared with patients with a PFI of 18–24 months.

As the majority of patients with advanced ovarian cancer will eventually relapse with incurable and terminal disease, there is significant unmet need for improved tools to aid earlier diagnosis and also

for establishing more effective alternative treatment options for the late stage resistant patient population. As such, there is a need for better first-line therapies that may delay or prevent relapse and improve survival rates. An unmet need also exists in the setting of recurrent disease, where currently used therapies have little impact on survival. As such the addition of a new drug on the market to current standard of care may impact significantly on patient management, given the current lack of effective treatment options once patients relapse.

High Grade Serous Ovarian Cancer (HGSOC) accounts for approximately 70% of malignant ovarian surface epithelial carcinoma in Europe and North America [9]. Mutant TP53 is a hallmark of HGSOC, resulting in deregulation of cell cycle checkpoints and uncontrolled tumor cell proliferation and thus represents a key driver event. Pathogenic TP53 mutations have been quoted as occurring in up to 96% of patients with HGSOC [4]. Rearrangements in TP53 have been shown to correlate significantly with resistance to chemotherapy, early relapse and shortened overall survival.

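### The interim model behind both accrual-stopping rules omits the three randomisation strata that the final test uses: a small, low-priority loss of efficiency if those strata are prognostic

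*Combined protocol and SAP*

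**What the plan says.** Section 9.7.1 models control event times with one vector that "represents the set of baseline hazard rates (events per month) within each segment". The segments are four time intervals, so the index is time and not stratum. Section 9.7.2 continues: "The event times for the treatment group is also modeled as piecewise exponential, with hazard rates" obtained by multiplying each control rate by exp(theta), with a single theta for all patients. No covariate or stratum-specific baseline appears in either section.

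This model feeds two rules. From 150 patients, accrual may stop for a small effect if Pr(HR < 0.8) is below 0.30 (9.8.3.2). From 200 patients, it may stop for predicted success if PPoS exceeds 0.95 (9.8.3.1). For PPoS, event times are imputed from the model only for patients without an observed event, and then "A stratified logrank test is performed on each imputed data set, and PPoS is equal to the proportion of imputed trials" reaching one-sided p below 0.023 (9.7.3.2).

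At the end, "a one-sided p-value is calculated for a stratified logrank test comparing treatment versus control" (9.5.2.1). The strata are PFI (two levels), BRCA status (two) and prior platinum lines (two), which are also the randomisation factors in 9.6 and 9.8.2. The text does not say why the interim model leaves them out.

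**The concern.** The interim model does not match the analysis it is meant to anticipate. Omitting prognostic factors from a hazard model pulls the treatment hazard ratio towards 1, because high-risk patients fail first, and do so faster on control, so the arms drift apart in risk mix. The small-effect rule would then judge an effective drug by a slightly weakened effect. PPoS would draw the remaining event times without regard to stratum and then test them within strata.

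At stake is how often accrual stops for the wrong reason, or fails to stop for the right one, when the drug works. The factors are recorded at randomisation, so any loss is avoidable without new data.

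**Working it through.** **Inputs from the documents.** Looks at 150, 200, 250, 300 and 350 patients, maximum 400, 1:1 allocation; final analysis 12 months after the last enrolment; one-sided level 0.023; Gamma(1,1) priors on the segment hazards and N(0, 0.5²) on theta; boundaries 0.30 and 0.95.

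**Assumptions.** Control median 11.3 months (the cited phase III result in 2.2 and 2.7, not stated as a design input), 15 patients a month (range 10 to 25), stratum prevalences and stratum hazard ratios as below, no dropout, PFS observed continuously, no CA-125 model.

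**1. The plan's own figure.** Section 9.8.4 gives power of about 0.70 at HR 0.70. By Schoenfeld's formula this needs 4(1.995 + 0.524)²/(ln 0.70)² = 25.4/0.1272 ≈ 200 events. Simulating the design with the model as written gives power of about 0.65 to 0.68 at 15 a month, 0.70 to 0.73 at 10 and 0.57 to 0.63 at 25. The stated figure is plausible. It cannot be reproduced exactly, because the visible text gives neither accrual nor the control curve.

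**2. Size of the dilution.** If the true hazard is λ_s·exp(theta·arm + b1·PFI + b2·lines + b3·BRCA) and the model fits λ_s·exp(theta·arm), the large-sample fitted HR (800,000 simulated patients) is:

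| Factor HRs (PFI/lines/BRCA) | True 0.70: n=150 | n=350 | True 0.80: n=150 | n=350 |
|---|---|---|---|---|
| none (1/1/1) | 0.698 | 0.701 | 0.800 | 0.801 |
| mild (1.4/1.2/0.8) | 0.701 | 0.704 | 0.799 | 0.803 |
| moderate (1.8/1.4/0.65) | 0.704 | 0.711 | 0.802 | 0.808 |
| strong (2.5/1.7/0.5) | 0.713 | 0.725 | 0.810 | 0.818 |

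The first look has about 33 events, so SE(log HR) ≈ 2/√33 = 0.348. The shift there is ln(0.704/0.70) = 0.0057 (moderate) or ln(0.713/0.70) = 0.0184 (strong), which is 1.6% or 5.3% of one SE.

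The plan's priors matter more. With no stratum effect, the mean posterior HR at the first look is already about 0.735. That is a net figure. The normal prior alone would give roughly exp[8.25/(8.25 + 4) × ln 0.70] = 0.79, where 8.25 = 33/4 and 4 = 1/0.5². The Gamma(1,1) priors, each acting like one extra control event in one month, pull it back down.

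**3. Effect on decisions.** Two simulations re-decided the same trials with and without the factors in the interim model, at within-stratum HR 0.70, median 11.3 months and 15 a month. A used 7,000 trials, prevalences 50/30/20% and factor HRs 1.5/1.3/0.7 (moderate) or 2.0/1.5/0.5 (strong). B used 3,000 trials, prevalences 50/30/25% and the factor HRs in step 2, and counts a small-effect stop as a failure.

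| Setting | Small-effect stop, without → with factors | Success stop | Power |
|---|---|---|---|
| A, moderate | 24.7% → 23.9% | 36.3% → 37.1% | 68.8% → 69.1% |
| A, strong | 25.2% → 23.7% | 35.7% → 37.9% | 69.0% → 69.5% |
| B, none | 24.9% → 24.7% | 37.9% → 38.4% | 66.3% → 66.2% |
| B, moderate | 26.6% → 25.9% | 34.7% → 37.0% | 65.5% → 65.9% |
| B, strong | 27.7% → 25.8% | 32.5% → 36.3% | 64.8% → 65.8% |

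Paired standard errors in A are 0.14 to 0.23 points. In B the no-effect row shows that about 0.5 point of the rise in success stops comes from the normal (Laplace) approximation used for the adjusted model. The largest power difference over 10 to 25 a month is 72.1 − 70.4 = 1.7 points (B, strong, 10 a month). In that setting small-effect stops go from 22.9% to 20.2% and success stops from 41.6% to 46.8%.

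**4. Null case.** At HR 1 the final test rejects in about 1.8% of trials under both models in A, and in 1.9% without against 2.0% with the factors in B (strong). All are below 2.5%.

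**The case against.** A four-segment model with one hazard ratio is a defensible, economical choice with about 33 events. Pr(HR < 0.8) is defined on that model's hazard ratio, and 0.30 is a chosen cut, so a marginal hazard ratio is a different quantity and not an error. This stands, and it is why the point is about efficiency. It does not explain why PPoS imputes without the strata and then tests within them.

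A reader might go further in four ways that the documents do not support.

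- **That the strata are known to be prognostic for PFS.** Section 2.2 links PFI to the chance of response when platinum is reintroduced. It gives no PFS hazard ratio for any factor, so every effect size above is assumed.
- **That both rules rest wholly on a diluted hazard ratio.** Only the small-effect rule does. In PPoS, observed events enter the stratified test directly, and 9.7.3.2 says patient-level CA-125 modelling will be added. Neither simulation includes CA-125, and A approximates PPoS without imputing patient by patient.
- **That interim decisions are materially distorted.** In A the stopping look or reason changes in 5.8% (moderate) or 10.6% (strong) of trials, but this counts changes in either direction; the net shifts are those in the table. In B, at 150 patients and 15 a month, the two models fall on opposite sides of 0.30 in only 1.0 to 2.1% of trials.
- **That the trial's conclusion is at risk.** Both rules only permit accrual to stop, follow-up may continue after a small-effect stop, and the final criterion does not use the model: "The treatment will be considered superior to control if the corresponding one-sided p-value is less than or equal to 0.023".

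The appendix with the operating characteristics is not in the public copy. It may include prognostic strata, and its absence is not held against the plan.

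**Conclusion.** The mismatch is real and visible in the text, and its direction is clear if the factors are prognostic for PFS. Under moderate to strong assumed effects, an 11.3-month control median and 15 patients a month, it costs an effective drug about 1 to 2 points in extra small-effect stops, 1 to 4 points in missed predicted-success stops and 0.3 to 1 point of power. Over accrual of 10 to 25 a month the power loss reaches 1.7 points at most. If the factors are not prognostic, nothing is lost by the present model and power is essentially the same with them added.

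This is a low-priority efficiency improvement. It is not an error in the final analysis or in type I error control.

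**What to change.** In 9.7.1 and 9.7.2, write the hazard as λ_s·exp(theta·arm + b1·PFI + b2·prior lines + b3·BRCA), with weak priors on b1 to b3, for example N(0, 1). Use this adjusted theta for Pr(HR < 0.8). In 9.7.3.2, impute each event-free patient's time from the hazard of her own stratum before the stratified logrank test. Keep the 0.30 and 0.95 boundaries and the final test.

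Section 9.7.3.2 says the CA-125 model is not yet in the simulations, so the operating characteristics need a further run in any case; check the adjusted model in the same run, with and without prognostic strata. If the sponsor prefers the simpler model, a sentence giving the reason and a simulation showing that the mismatch is negligible would also close the point.

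Cost: revised wording, three more parameters on about 33 events at the first look, changes to the interim code, and the simulation run. No extra patients, visits or data are needed.
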